Multiparametric high-resolution sonography with Color/Power-Doppler, elastography and contrast-enhanced sonography for an improved detection and characterization of breast tumors.

1. Introduction

The value of mammography in breast cancer screening and diagnosis is unquestioned. Yet mammography has certain limitations, especially in women with dense breasts, with a considerable decrease in sensitivity and specificity (1). Ultrasound (US) is an established adjunct to mammography for further characterization of mammographically detected breast lesions, for lesion detection in women with dense breasts (ACR 3 and 4) (2), and due to the lack of ionising radiation is the method of choice in younger women.

When using established criteria for the assessment of the probability of malignancy with B-mode US (2, 3), it has a high diagnostic performance with sensitivities ranging from 94 to 95.4% and specificities ranging from 83 to 87.4% (4, 5). In B-mode breast US a malignant mass is typically round or irregularly shaped, vertically orientated to the skin, markedly hypoechoic and demonstrates a non circumscribed margin and posterior shadowing. Yet there are several benign or pre- cancerous lesions that demonstrate one or more of these characteristics, whereas malignant tumors do not always present with a typical morphology. In order to improve sonographic detection and especially characterization of breast lesions, other US examination modes and techniques apart from standard B-mode such as elastography, Color Doppler, contrast-enhanced and 3D imaging have been developed and are currently under investigation.

- Elastography measures the strain induced by probe compression on the breast. Based on the fact that breast cancer is in most cases stiffer than unaffected breast parenchyma, several studies have demonstrated an increase in specificity of conventional US by the addition of elastography (4-9).
- One of the hallmarks of malignant tumors is tumor neoangiogenesis. Therefore studying the vascularization features of breast tumors by the means of Color and Power Doppler US helps to differentiate breast cancer from benign lesions (9-12).
- Contrast-enhanced US assessing kinetic properties of breast tumors, especially with the use of second generation contrast agents, has been

investigated by several authors and shown promising results (13-19). Nevertheless different contrast agents and dosages have led to a certain degree of discordance among publications (16, 17).

- 3D imaging obtains reconstructions in the coronal plane and allows an improved depiction of the tumor interface, a valuable sonographic descriptor for differentiation of benign and malignant lesions (3, 20-22).

Cho et al (9) have shown that the addition of elastography and Color Doppler to B-mode US can lead to a higher accuracy and sensitivity. Yet up to now there are no published studies evaluating the possible benefit of a multiparametric approach by adding elastography, Color Doppler, contrast-enhanced and 3D studies to B-mode US.

1.1 State of the art

2D B-mode ultrasound has been established as an adjunct to mammography for both screening and diagnostic purposes in women with dense breast parenchyma, for further characterization of clinically or mammographically detected lesions, for follow up and for guiding interventional procedures (2, 23). Elastography, Color Doppler and contrast-enhanced sonography are applied for an improved differentiation of benign from malignant lesions, whereas 3D ultrasound mainly offers better conspicuity of lesions and their interface with normal surrounding tissue.

1.2 Clinical perspective and study aim

In this prospective study we will perform multiparametric high resolution ultrasound in patients with known suspicious breast lesions (BI-RADS 4 and 5). We will acquire morphologic by conventional B-mode and 3D US and functional information about the lesions by examination of tumor vascularity and structure as expressed by means of stiffness. It can be expected that with this multiparametric US imaging an increased sensitivity and especially specificity of US of the breast can be achieved.

2. Patients and Methods

Over a period of 24 months 120 patients with breast lesions categorized as BI-RADS 4 and 5 (3) will be included in this prospective study- that means patients with suspicious lesions, planned to undergo an image-guided biopsy or surgery. This number of patients is necessary for a hypothesized improvement of the AUC by 10% (from 0.8 to 0.9) with a type I error of 5% and a type II error of 20%. The recruitment of patients will take place immediately after a breast clinical or imaging examination (mammography, ultrasound or MRI of the breast) demonstrating a suspicious breast lesion as described previously. All patients will be examined with multiparametric ultrasound. Contrast-enhanced examination will be conducted subsequently to the non contrast-enhanced one. The whole examination time will be approximately 30 minutes. Histopathology with either image-guided biopsy or surgery will be used as the standard of reference. Both in situ and invasive carcinomas will be regarded as a malignant (positive) result whereas benign and precursor lesions will be regarded as a benign (negative) result. In case of an image-guided biopsy, this will be performed immediately after the sonographic examination, whereas in the cases of planned surgery, this will be performed according to the planning of the respective Departments of Surgery or Gynecology.

2.1 Inclusion criteria

- Clinical, mammographic, MR-tomographic and/or ultrasonographic verification of a suspicious breast lesion (BIRADS 4 and 5)
- Age > 18 years
- Written informed consent
- Histopathological verification of the lesions either by core biopsy or by surgical excision

2.2 Exclusion criteria

- Unstable or non-compliant patients
- Pregnant or lactating patients or patients with suspected pregnancy

- Known contraindication to the intravenous administration of US contrast agents
- Acute or chronic renal insufficiency
- Pre- or post-transplant patients

2.3 Imaging technique and evaluation

All patients will be examined using a CE certified Siemens Accuson S3000 ultrasound device, which is used for routine examinations in our department.

2.3.1 B-mode 2D/3D examination

2.3.1.1 Technique

For the B-mode examinations an 18L6HD linear transducer will be used. The settings that will be used are the following: Dynamic Range 75 dB, Custom Tissue Imaging 1, ASC 3, High Dynamic Tissue Contrast Enhancement, Margin 3, Persistence 3 and Space/Time encoding 3. For 3D imaging a data volume will be acquired and coronal plane images will be saved.

2.3.1.2 Image evaluation

Image evaluation of the B-mode ultrasound will be performed according to the revised ACR BI-RADS lexicon for ultrasound 5th edition, (3). Lesions will be evaluated for shape (oval, round or irregular), orientation (parallel or not), margin (circumscribed, microlobulated, indistinct, angular or spiculated), internal echogenicity (anechoic, hyperechoic, isoechoic, hypoechoic, heterogeneous or complex cystic and solid) and posterior acoustic features (none, enhancement, shadowing or combined pattern). Additionally on the coronal plane the presence or absence of retraction will be noted (22). The number and exact size of lesions in all 3 dimensions will be documented. Finally the likelihood of malignancy will be reported according to the ACR BI-RADS lexicon (3), with 4a = low suspicion for malignancy; 4b = moderate suspicion for malignancy; 4c = high suspicion for malignancy and 5 = highly suggestive of malignancy.

2.3.2 Elastography examination

2.3.2.1 Technique

For Acoustic Radiation Force Impulse (ARFI) elastography a 9L4 linear transducer and the “Virtual Touch IQ™” mode will be used, with following settings: Dynamic Range 65dB, Space/Time encoding 3, Spatial Compounding Off and Medium Dynamic Tissue Contrast Enhancement, whereas the velocity scale will be set from 0,5 to 10 m/sec. The images will be obtained by using a rectangular ROI including the lesion and at least 5 mm of normal surrounding tissue. Three 2 x 2 mm quantification ROIs will be placed in the lesion in order to measure the shear-wave velocity inside the lesion, whereas another equally big quantification ROI will be placed on fat tissue at the same depth to measure shear-wave velocity in fat tissue (24, 25).

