2.3.2.2 Image evaluation

The shape (oval, round or irregular) and homogeneity (very, reasonably or not homogeneous) of the lesion as well as the elasticity ratio (lesion to fat elasticity) will be assessed, as has been proposed by Berg et al for shear-wave elastography (24). Using three ROIs placed in the lesion, the mean, maximum and minimum elasticity of the lesion (measured as shear-wave velocity in m/sec) as proposed by Berg et al and Bai et al (25) will be calculated (24).

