For the assessment of treatment response, functional imaging data of the baseline examination and of the examinations after the 1st, 2nd, 4th and 6th (+/- 8th) cycle will be compared for therapy-induced changes of both lesion morphology and functional capabilities by two experienced radiologists independently.

The statistical evaluation will be performed as described in the original study protocol.

CHANGES IN THE STUDY PROTOCOL

- Additional mp US examinations after the first, second, fourth and sixth (and after the eighth, if 8 NAC cycles are necessary) cycle of NAC.
- Correlation of qualitative and quantitative imaging parameters with histopathological tumor grade, microvascular density, hormone receptor status, HER2-neu, proliferative indices and gene expression profile before and after NAC.

4. Literature

2. Stavros AT. Breast ultrasound. Philadelphia: Lippincott, Williams and Wilkins; 2004.

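### The elasticity ratio divides a lesion value drawn from three ROIs by a single fat ROI, so the denominator's error is never averaged; adding fat ROIs is a cheap improvement of uncertain, probably modest size

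*Combined protocol and SAP*

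**What the plan says.** Section 2.3.2.1 sets the measurement scheme. In the lesion: "Three 2 x 2 mm quantification ROIs will be placed in the lesion in order to measure the shear-wave velocity inside the lesion". In the reference tissue: "another equally big quantification ROI will be placed on fat tissue at the same depth to measure shear-wave velocity in fat tissue". No repeat fat reading is described.

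Section 2.3.2.2 then says that "the elasticity ratio (lesion to fat elasticity) will be assessed". It also derives the mean, maximum and minimum velocity from the three lesion ROIs, but does not say which of these is the numerator of the ratio. Neither section gives a standard deviation, coefficient of variation (CV) or repeatability figure for a single ROI in either tissue.

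The amendment on neoadjuvant chemotherapy (Part 2, 40 patients) keeps the image analysis of the main protocol (Part 1). Baseline findings and those after cycles 1, 2, 4 and 6, and 8 where given, "will be compared for therapy-induced changes of both lesion morphology and functional capabilities by two experienced radiologists independently". The same three-to-one scheme therefore applies at baseline and at up to five later examinations.

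**The concern.** In a ratio, a relative error in the denominator passes in full to the result, and averaging in the numerator does nothing to reduce it. The plan takes three readings in the lesion and relies on one 2 x 2 mm reading for the tissue that scales them.

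Measurement noise in the ratio pulls its AUC towards 0.5. That matters most in Part 2, which has 40 patients and looks for functional change as early as the third day after the first cycle, before shrinkage is visible. Each change from baseline contains two single fat readings, and one baseline fat reading is reused in up to five comparisons for the same patient. Some of this noise could be removed on an image that is already being acquired.

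**Working it through.** The plan states no figure for ROI error, so there is nothing of its own to reproduce. The size has to be worked out under stated assumptions and shown as a range.

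**Inputs from the documents.** Three lesion ROIs and one fat ROI of equal size (2.3.2.1); a lesion-to-fat ratio (2.3.2.2); repeated use by visit (amendment).

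**Assumptions.** The numerator is the lesion mean. c is the CV of one fat ROI and k is the lesion CV divided by the fat CV. ρ is the error correlation between ROIs in the same tissue. Errors are independent between tissues and between visits.

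**Variance of the log ratio (delta method).** With f = (1 + 2ρ)/3:

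- one fat ROI: V1 = c²(k²f + 1)
- three fat ROIs averaged: V3 = c²(k²f + f)
- share due to the single fat ROI: 1/(k²f + 1)
- fall in error SD: 1 − √(V3/V1)

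For k = 1 and ρ = 0, f = 1/3. Then V1 = 1.333c² (SD 1.155c) and V3 = 0.667c² (SD 0.816c). The fat share is 1/1.333 = 75%, and the SD falls by 1 − 0.816/1.155 = 29%.

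| k | ρ | Fat share, one ROI | SD, one fat ROI | SD, three fat ROIs | Fall in SD |
|---|---|---|---|---|---|
| 1 | 0 | 75% | 1.155c | 0.816c | 29% |
| 1 | 0.5 | 60% | 1.291c | 1.155c | 11% |
| 2 | 0 | 43% | 1.528c | 1.291c | 15% |
| 2 | 0.5 | 27% | 1.915c | 1.826c | 5% |

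The fat reading supplies more than half the error variance only while k is below √(3/(1 + 2ρ)): 1.73 at ρ = 0, 1.22 at ρ = 0.5 and 1.00 at ρ = 1. If the numerator is the lesion maximum or minimum instead of the mean (simulation, 1,000,000 log-normal draws, ρ = 0, fat CV 10%), the fat share is 64% at k = 1 and 31% at k = 2.

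**Change from baseline.** The variance is 2V, because both the lesion and the fat error enter once per visit. At c = 10%, k = 1, ρ = 0 the SD of the change is √(2 × 0.01333) = 0.163. The fat share stays at 75%.

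**Illustration for Part 2.** Assume that the log-change in the ratio would have an AUC of 0.90 without measurement error, and that the SD of the true log-change is s = 0.3. Then AUC = Φ(d·s / √(s² + 2V) / √2), with d = √2 × z(0.90) = 1.812. For c = 10%, k = 1, ρ = 0 and one fat ROI: 1.812 × 0.3 / √(0.09 + 0.0267) / √2 = 1.126, and Φ gives 0.870. With three fat ROIs, 0.0133 replaces 0.0267 and the AUC is 0.884.

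| k | ρ | AUC at c = 10%, one v three | AUC at c = 20%, one v three | Gain |
|---|---|---|---|---|
| 1 | 0 | 0.870 v 0.884 | 0.807 v 0.845 | 0.014 to 0.038 |
| 1 | 0.5 | 0.863 v 0.870 | 0.792 v 0.807 | 0.007 to 0.015 |
| 2 | 0.5 | 0.829 v 0.834 | 0.733 v 0.740 | 0.005 to 0.007 |

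At c = 5% with k = 1 and ρ = 0 the gain is negligible (0.892 v 0.896).

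**The case against.** Much of the case on the other side stands.

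- **The fat reading need not dominate.** A reader might infer from the three-to-one imbalance that the fat reading supplies most of the ratio's error. The documents do not support that as a fact, because it needs similar relative error in lesion and fat. Section 2.3.2.2 itself grades "homogeneity (very, reasonably or not homogeneous) of the lesion", so greater scatter in the lesion is plausible.
- **Entering twice adds nothing specific to fat.** A reader might also infer that change from baseline makes the fat reading worse relative to the lesion. The count of two is right, but the lesion error enters twice as well, so the fat share does not change.
- **The lesion ROIs have their own purpose.** They yield a mean, maximum and minimum, and no such summary of fat is sought. The imbalance is therefore not plainly an oversight. That explains the three lesion ROIs, but it does not make a single denominator reading more precise.
- **The ratio is a small part of the plan.** It is one of many B-mode, Doppler, elastography and contrast parameters, and no endpoint names it. Lesion velocities are analysed in their own right, so early change in stiffness can be studied with no fat error at all.
- **Space for more ROIs is not assured.** Section 2.3.2.1 guarantees at least 5 mm of normal tissue around the lesion, not 5 mm of fat, while three 2 mm ROIs side by side need 6 mm. If the number that fits varies, precision will vary between patients and possibly between visits.

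None of this removes the gain. Under the model, averaging more fat ROIs never increases the error, and the benefit vanishes only if errors within a tissue are perfectly correlated. Nor does having two radiologists supply a second fat reading as the text stands, since it does not say that each places their own ROIs.

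**Conclusion.** The point holds as an optional gain in precision. The denominator of the elasticity ratio rests on one unreplicated reading at every examination. Averaging three fat ROIs would lower the ratio's error SD by between 5% and 29% over the cases examined. In the Part 2 illustration the AUC gain at fat CV 10 to 20% runs from 0.005 to 0.038, and the upper end needs equal and independent ROI errors.

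These figures rest on assumed values of k, ρ and c, on the lesion mean as numerator and, for the AUC, on an assumed error-free value of 0.90 and SD of 0.3. The 0.9 in the amendment is the improved AUC hypothesised for that part of the study, not a value for this ratio alone. No gain has been worked out for Part 1. Because the ratio is one of many parameters and lesion velocities carry no fat error, no main conclusion of the study is shown to depend on this point. Separately, the unstated numerator is a small gap in definition that the same edit can close.

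**What to change.** - In 2.3.2.1, place up to three 2 x 2 mm ROIs in fat at the lesion's depth on the image already acquired. Use their mean as the denominator and record how many were placed.
- In 2.3.2.2, state that the ratio is mean lesion velocity divided by mean fat velocity.
- For visit comparisons under the amendment, aim for the same number of fat ROIs at each of a patient's examinations.

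The cost is a short wording change and up to two more ROI placements per elastography image, with slightly more measurement time and no extra patient or reader. The downside is that fewer than three fat ROIs may fit in some breasts, so precision would differ between patients; recording the number makes that visible. Label: cheap improvement.

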2.3.2.2 Image evaluation

The shape (oval, round or irregular) and homogeneity (very, reasonably or not homogeneous) of the lesion as well as the elasticity ratio (lesion to fat elasticity) will be assessed, as has been proposed by Berg et al for shear-wave elastography (24). Using three ROIs placed in the lesion, the mean, maximum and minimum elasticity of the lesion (measured as shear-wave velocity in m/sec) as proposed by Berg et al and Bai et al (25) will be calculated (24).

2.3.3 Color/Power Doppler US examination

2.3.3.1 Technique

For Color/Power Doppler US examination a 18L6HD linear transducer will be used. The examination settings for the Color Doppler US examination will be as following: Dynamic Range 70dB, Low Flow, Smooth 3, Space/Time encoding 5, Persistence 2, Filter 0 and a PRF of 488. The settings for the Power Doppler examination will be the following: Dynamic Range 70dB, Low Flow, Smooth 2, Space/Time encoding 5, Persistence 2, Filter 1 and a PRF of 488. A ROI slightly bigger than the lesion will be used and cine clips of at least 5 sec per case will be saved.

2.3.3.2 Image evaluation

We will evaluate the number and distribution of vessels within and around the lesion according to the schemes proposed by Raza et al (12) and Moon et al (15). A score of 0-2 will be attributed as follows: 0= no visible vessels in the lesion; 1= one or two peripheral or central vessels; 2= three or more peripheral or central vessels or one or more penetrating vessels. Furthermore the morphology of the vessels will be assessed, as A= regular (uniform in caliber and course) or B= irregular (caliber irregularities, tortuous course) (26).

2.3.4 Contrast-enhanced examination

2.3.4.1 Technique

The contrast agent used will be a CE certified standard US contrast agent approved for breast diagnostics by the Austrian Federal Office for Safety in Health Care (27), injected intravenously as a bolus at a dose of 0.03 ml (0,24 µl of sulphur hexafluoride microbubbles) per kg of body weight. Every injection will be followed by a flush with 5 ml of sodium chloride 9 mg/ml (0.9%) solution. The contrast-enhanced US examinations will be conducted using a 9L4 linear transducer and the following settings: Frame Rate 23 l/sec, Dynamic Range 80dB, Margin 3, Persistence 3, Space/Time encoding 3, MI 0,06 and MIF 0,05.

2.3.4.2 Image evaluation

For the evaluation of contrast-enhanced examinations the number and distribution as well as the morphology of vessels will be reevaluated, similarly as in the pre- contrast studies (12, 15, 26). Furthermore the degree of enhancement will be characterized as minimal (no additional vessels), moderate (one or two additional vessels) or marked (three or more additional vessels), as proposed by Moon et al (15). Finally dynamic features, i.e. Time To Peak (TTP) enhancement and the time until the elevated signal returns to baseline levels, will be noted (17). Any cases of prolonged (>5 min) enhancement will be recorded, as has been proposed by Jung et al (18).

2.4 Evaluation of multiparametric ultrasonographic data

After evaluation of US data for clinical purposes two radiologists blinded to the findings of the other imaging modalities or the histopathological diagnosis, will evaluate the multiparametric US data acquired according to the above mentioned criteria. Results of multiparametric US will be compared to the results of B-mode ultrasound.

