2.5 Statistical evaluation

A McNemar test will be applied to the B-mode ultrasound alone and B-mode ultrasound with additional ultrasonographic examinations positive and negative results to determine statistical independence. ROC analysis will be performed to estimate the overall performance of B-mode ultrasound and multiparametric ultrasound. Using the histopathological data the numbers of true-negative (TN), true-positive (TP), false-negative (FN) and false-positive (FP) results for B-mode ultrasound and multiparametric US will be obtained and sensitivity, specificity, accuracy, positive predictive value (PPV) and negative predictive value (NVP) for both methods will be calculated.

3. Timetable

September 2015	Obtaining IRB approval
September 2015 to April 2017	Multiparametric ultrasound examinations according to protocol
May/June 2017	Statistical evaluation
July to September 2017	Preparation and submission of manuscripts

AMENDMENT TO THE STUDY PROTOCOL

Treatment of early breast cancer is usually surgical, comprising breast-conserving surgery for small, unifocal tumors, or mastectomy for larger or multicentric tumors. However, in women with locally aggressive disease or whose tumors display features that are predictive of early recurrence, neoadjuvant chemotherapy (NAC) is given to reduce the risk of recurrence. The early identification of chemotherapy responders and non-responders is crucial

in order to allow chemotherapy scheme modifications or changes to surgery or hormonal therapy, and thus provide optimal patient outcomes. Yet tumor response to NAC can be very different, resulting in fibrosis, concentric shrinking, fragmentation or change in the density of malignant tissue. All of these may affect the evaluation of residual tumor size (28).

Evaluation of tumor response to NAC is routinely done by using solely morphologic criteria (size reduction in mammography or B-mode ultrasound (US)), with US being more accurate than mammography in the evaluation of residual tumor size after NAC (28), showing a moderate correlation with the final histopathologic tumor size (29).

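### The plan does not clearly define an overall multiparametric rating, or a positivity cut-off for either method, although the AUC comparison, the 2x2 tables and McNemar's test all need them

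*Combined protocol and SAP*

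**What the plan says.** Section 2 (Patients and Methods) justifies 120 patients by a "hypothesized improvement of the AUC by 10% (from 0.8 to 0.9"), with type I error 5% and type II error 20%.

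Section 2.3.1.2, within the B-mode 2D/3D examination, ends with an overall BI-RADS category: 4a, 4b, 4c or 5. The evaluation sections for the added modes list separate items:

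- Elastography (2.3.2.2): shape, homogeneity, lesion-to-fat ratio, and mean, maximum and minimum velocity (6 items).
- Doppler (2.3.3.2): vessel score 0-2 and vessel morphology (2).
- Contrast (2.3.4.2): vessel score, morphology, degree of enhancement, time to peak, time to baseline, and enhancement beyond 5 minutes (6).

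That makes 14 descriptors, six of them continuous.

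Section 2.4 has two radiologists, blinded to histology and to the other imaging modalities, who "will evaluate the multiparametric US data acquired according to the above mentioned criteria". It then states: "Results of multiparametric US will be compared to the results of B-mode ultrasound". In section 2.5, "ROC analysis will be performed to estimate the overall performance of B-mode ultrasound and multiparametric ultrasound", and McNemar's test is applied to B-mode alone and "B-mode ultrasound with additional ultrasonographic examinations positive and negative results to determine statistical independence". Sensitivity, specificity, accuracy and predictive values follow for both methods. The only definition of a positive result, in section 2, concerns histopathology. The amendment takes over the image analysis and statistics of the original protocol.

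**The concern.** An AUC needs one ordered score per lesion and method. A 2x2 table or McNemar's test needs one yes/no result per lesion and method. B-mode has the ordered score but no cut-off. Multiparametric US has neither in explicit form, yet one of the two AUCs behind the sample size is presumably its AUC.

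Readers who follow the descriptor lists literally might never record the rating that the main comparison needs. Someone would then have to construct it. Blinding protects the descriptor readings, but not a rule or cut-off chosen after those readings are linked to histology. Such a choice can trade sensitivity against specificity without new diagnostic information. A combination fitted on the same lesions also favours multiparametric US over a fixed B-mode category.

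**Working it through.** **1. The plan's own figure.** Inputs from section 2: AUC 0.8 and 0.9, alpha 5% (sidedness not stated; two-sided used here), power 80%. The malignant share and the correlation r between the two AUCs are not given, so both are assumed.

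Hanley-McNeil variance with n1 malignant and n0 benign lesions:
V(A) = [A(1-A) + (n1-1)(A/(2-A) - A²) + (n0-1)(2A²/(1+A) - A²)] / (n1·n0).

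Paired difference: V = V(0.8) + V(0.9) - 2r√[V(0.8)·V(0.9)]. The required N satisfies 0.10/√V = 1.960 + 0.842.

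- Malignant share 0.3-0.7: N = 219-338 at r = 0 and 117-177 at r = 0.5.
- Share 0.6 with r = 0.5 gives 117; share 0.4 with r = 0.6 also gives 117.
- At N = 120, share 0.5 and r = 0.5, the standard errors are 0.0406 and 0.0293, and 0.0363 for the difference. Then 0.10/0.0363 - 1.960 = 0.80, so power is 78.7%. It is 51.5% at r = 0 and 86.1% at r = 0.6.

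So 120 is attainable. But r depends on how the multiparametric score is formed, which the plan does not settle.

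**2. The cut-off.** If all listed categories (4a to 5) count as positive, every lesion is positive: sensitivity 100%, specificity 0%. For other cut-offs, take three assumed splits over 4a/4b/4c/5:

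| Split | Benign | Malignant | AUC | Sens/spec at ≥4b | Sens/spec at ≥4c |
|---|---|---|---|---|---|
| A | .57/.25/.14/.04 | .13/.20/.30/.37 | 0.806 | 87/57 | 67/82 |
| B | .72/.20/.06/.02 | .22/.21/.26/.31 | 0.805 | 78/72 | 57/92 |
| C | .40/.35/.20/.05 | .08/.20/.27/.45 | 0.799 | 92/40 | 72/75 |

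AUC = Σ mᵢ(Σ_{j<i} bⱼ + bᵢ/2). For A: .13×.285 + .20×.695 + .30×.89 + .37×.98 = 0.806. Moving the cut-off one category changes sensitivity by 20-21 points and specificity by 20-35.

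**3. The combination rule.** Add to B-mode at ≥4b one yes/no result each from elastography, Doppler and contrast. Each is assumed 80% sensitive and 80% specific, and independent given histology. The chance of at least 1, at least 2, or all 3 added results positive is .992/.896/.512 in malignant and .488/.104/.008 in benign lesions.

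Split A, 2 of 4 positive:
- sensitivity = .87×.992 + .13×.896 = 98.0%
- specificity = 1 - (.43×.488 + .57×.104) = 73.1%

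Split A, 3 of 4 positive:
- sensitivity = .87×.896 + .13×.512 = 84.6%
- specificity = 1 - (.43×.104 + .57×.008) = 95.1%

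| Split | 2 of 4 | 3 of 4 | Shift in sens/spec (points) |
|---|---|---|---|
| A | 98.0/73.1 | 84.6/95.1 | 13/22 |
| B | 97.1/78.8 | 81.2/96.5 | 16/18 |
| C | 98.4/66.6 | 86.5/93.4 | 12/27 |

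Varying the 80% over 70-90% gives shifts of 4-24 and 9-34 points.

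**4. McNemar's test.** Assume binormal scores with AUC 0.8 and 0.9, latent correlation 0.5 and 60 malignant/60 benign lesions. Changing only the cut-offs moves the exact test's rejection rate:
- both methods at specificity 0.5: 11%
- B-mode at 0.5, multiparametric at 0.75: 77%, with net fewer positives
- B-mode at 0.75, multiparametric at 0.5: about 100%, with net more positives

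**5. A fitted combination.** Simulated trials of 60/60 lesions (1000 per cell). A logistic model on the B-mode category plus q pure-noise descriptors is fitted and tested on the same lesions. The gain in apparent AUC across the three splits, against a planned gain of 0.10, is:

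| q | Apparent gain |
|---|---|
| 1 | 0.009-0.011 |
| 2 | 0.015-0.018 |
| 5 | 0.027-0.032 |
| 14 | 0.057-0.065 |

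Ten-fold cross-validation removes it (change -0.044 to +0.001).

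**The case against.** The best reply is that section 2.4 may already imply the rating. Two blinded radiologists evaluate the full data by criteria that include the 4a-5 category, and section 2.5 speaks of B-mode together with the additional examinations. That fits a reader who re-assigns a category with all modes in view. On that reading the multiparametric ROC curve is available and only the cut-off is missing. The reading is plausible, but the text does not state it, and the category is defined under B-mode only. A reader might infer that the AUC comparison cannot be produced at all; the documents do not support going that far.

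A reader might also infer that the rule will be chosen once histology is known. Biopsy results would exist by then: "In case of an image-guided biopsy, this will be performed immediately after the sonographic examination", and the timetable puts statistics in May/June 2017, after examinations end. But this shows when the analysis is run, not when a rule is set. No passage says the rule waits for histology, so the risk is conditional.

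The illustrations rest on assumed accuracies, category splits and a 50% malignant share. Conditional independence was not varied, although contrast re-scores the vessels already scored on Doppler. The plan names no fitted model. These are fair limits on the sizes, not on the gap.

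Finally, the Introduction speaks of "adding elastography, Color Doppler, contrast-enhanced and 3D studies to B-mode US", which might suggest an unsettled comparator. But the title, sections 1.1 and 1.2 and the amendment favour 3D on the B-mode side, and section 2.3.1.1, under B-mode, says "For 3D imaging a data volume will be acquired and coronal plane images will be saved". This is a point of wording.

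**Conclusion.** The concern holds in this form: the plan does not clearly state an overall multiparametric rating or combination rule, and gives no positivity cut-off for either method. The B-mode ROC curve can be drawn as planned. The 2x2 tables and McNemar's test cannot be run without a cut-off, and the obvious BI-RADS 4/5 cut-off fails on the listed categories (0% specificity).

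If the rule or cut-off is set after linkage to histology, sensitivity and specificity can move by some tens of points on unchanged readings. A combination fitted and tested on the same lesions would inflate the multiparametric AUC by about 0.01, 0.03 or 0.06 with 1, 5 or 14 noise descriptors. The effect is thus minor with one or two descriptors and more than half the planned gain with all 14. These sizes depend on the assumptions shown above.

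Two stronger conclusions are not supported. The sample size of 120 is not shown to be wrong, because it can be reached under plausible values of the unstated inputs. Nor can a false-positive rate be assigned to this plan. A DeLong test in the 14-descriptor simulation rejects in 82-92% of trials (1-3% with one descriptor), but the plan specifies neither that model nor that test.

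The gap should be closed before reading starts, because it touches the comparison on which the trial is sized.

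**What to change.** For part 1:

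- **Section 2.4.** Have the same two blinded readers each record and lock an overall B-mode category, then an overall multiparametric category on the same ordinal scale, before the readings are linked to histology. Use these ratings for the paired AUC comparison.
- **Section 2.5.** Fix one common cut-off for both methods before reading starts, for example ≥4b. It serves the analysis only and is not a biopsy rule. State how the two readers' results enter the 2x2 tables and McNemar's test, and report the other category boundaries as secondary.
- **Fitted combinations.** Report any of these as secondary, with a cross-validated or optimism-corrected AUC.

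Clarifications only: state whether coronal 3D belongs to the B-mode comparator, and whether categories below 4a may be used, since lesions may enter on clinical, mammographic or MR findings.

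The amendment (40 patients, AUC 0.7 to 0.9) needs its own prespecified response score, because a malignancy category does not measure treatment response.

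Cost: one extra score per reader and lesion, a sequential lock on the read form, and possibly a less favourable multiparametric AUC than a rule built on the same lesions would give. No additional examinations are needed.
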